## 15. EFFICACY OUTCOMES

### 15.1. PRIMARY EFFICACY

#### 15.1.1. PRIMARY EFFICACY ENDPOINT AND DERIVATION

For the double-blind portion (Part A), the primary efficacy variable is change from baseline in rater-administered MADRS total score to Week 6 (Day 43). The MADRS is a 10-item checklist designed to measure the overall severity of depressive symptoms. The MADRS individual items are rated by a qualified site rater at each site on a scale of 0 to 6 in which a score of 6 represents the most severe symptoms for each item assessed. The MADRS total score is the sum of all 10 items and ranges from 0 to 60. If one or more items are missing at a visit, the total score will also be set to missing for that visit.

In addition to the rater-administered MADRS assessment, a computer-administered MADRS assessment will be conducted. At screening, the computer-administered MADRS assessment will be conducted prior to the rater-administered one. At all other visits, the rater-administered MADRS assessment will be conducted first. Computer-administered MADRS scores will be compared to the ones from the rater-administered MADRS assessment on an ongoing basis as part of a remote quality assurance program.

#### 15.1.2. MISSING DATA METHODS FOR PRIMARY EFFICACY ENDPOINT

The primary analysis method for evaluating the primary efficacy endpoint is the likelihood-based analysis of repeated measures, MMRM, described in details in [Section 15.1.3](#). The use of MMRM inherently implies that the treatment effect on the change from baseline in the rater-administered MADRS total score will be similar for the subjects who withdraw and for those who complete the study in their respective treatment groups, conditional on the outcomes observed prior to withdrawal (MAR assumption). To challenge the robustness of the MAR assumption, sensitivity analyses which utilize multiple imputations and a different assumption about unobserved outcomes will be performed, as detailed in [Section 15.1.4](#).

#### 15.1.3. PRIMARY ANALYSIS OF PRIMARY EFFICACY ENDPOINT

The treatment effect on the Part A primary efficacy endpoint will be evaluated using an MMRM model. The model will include the change from baseline at each pre-specified timepoint as the response variable and study visit, the bipolar disorder stratification variable, baseline MADRS total score, site (or pooled site), baseline MADRS total score-by-study visit interaction, treatment (ITI-007 40 mg, ITI-007 60 mg, placebo), and treatment-by-study visit interaction. An unstructured covariance matrix will be used to model the correlation among repeated measurements within subject.

[REDACTED]

The Kenward-Rogers method will be used to estimate the denominator degrees of freedom. The treatment and treatment-by-time interaction terms allow for comparisons of the treatment groups at each of the following time points: Weeks 1, 2, 3, 4, 5, and 6 (Days 8, 15, 22, 29, 36, and 43). Treatment differences will be evaluated via contrasts for the time-by-treatment factor. This methodology will be used to compare the treatment groups versus placebo for change from baseline at each time point.

The change from baseline to Week 6 (Day 43) will be used for the primary efficacy analysis, and will be performed for the ITT Set [REDACTED].

[REDACTED]

[REDACTED]

[REDACTED]

Estimates of model parameters will be presented, as well as least-squares mean (LSM) estimates for change from baseline in MADRS score, standard errors and 95% confidence intervals (CI) for LSMs will be presented by treatment group and time point. Contrast estimates (LSMs) for between-group comparisons (ITI-007 60 mg vs. placebo and ITI-007 40 mg vs. placebo), the corresponding standard errors, 95% CIs, effect sizes, and p-values will be presented for each visit. Effect size will be calculated for each ITI-007 dose group (vs. placebo)

as 
$$\frac{\text{LS Mean Difference}}{\text{Pooled estimate of within patient error standard deviation}}$$
.

[REDACTED]

[REDACTED]

[REDACTED]

[REDACTED]

the first time in the history of the world, the people of the United States have been called upon to determine whether they will submit to the law of force, and give up the God-given right of self-government, or whether they will, in the language of their Declaration of Independence, "hold these truths to be self-evident, that all men are created equal, that they are endowed by their Creator with certain unalienable Rights, that among these are Life, Liberty and the pursuit of Happiness—that to secure these rights, governments are instituted among men, deriving their just powers from the consent of the governed, that whenever any Form of Government becomes destructive of these ends, it is the Right of the People to alter or to abolish it, and to institute new Government, laying its foundation on such principles, and organizing its powers in such form, as to them shall seem most likely to effect their Safety and Happiness."

Figure 1. The four main components of the model: the population of the city, the population of the region, the population of the country, and the population of the world.

1000 2000 3000 4000 5000 6000 7000 8000 9000 10000

10.1007/s00332-010-9000-0

[REDACTED]

[REDACTED]

[REDACTED] [REDACTED] [REDACTED] [REDACTED] [REDACTED] [REDACTED] [REDACTED]

[REDACTED]

[REDACTED]

[REDACTED] [REDACTED] [REDACTED] [REDACTED] [REDACTED] [REDACTED] [REDACTED]

[REDACTED]

[REDACTED]

[REDACTED]

[REDACTED]

[REDACTED]

[REDACTED]

[REDACTED]

[REDACTED]

[REDACTED]

[REDACTED]

[REDACTED]

[REDACTED]

[REDACTED]

[REDACTED]

[REDACTED]

[REDACTED]

[REDACTED]

[REDACTED]

[REDACTED]

[REDACTED]

[REDACTED]

[REDACTED]

[REDACTED]

[REDACTED]

[REDACTED]

[REDACTED]

[REDACTED]

[REDACTED]

[REDACTED]

[REDACTED]

[REDACTED]

[REDACTED]

[REDACTED]

[REDACTED]

[REDACTED]

[REDACTED]

[REDACTED]

[REDACTED]

[REDACTED]

[REDACTED] [REDACTED]

[REDACTED]

[REDACTED] [REDACTED]

[REDACTED]

[REDACTED] [REDACTED] [REDACTED] [REDACTED] [REDACTED]

[figure not shown]
[REDACTED]

[REDACTED] [REDACTED] [REDACTED] [REDACTED]

[REDACTED]

[REDACTED]

[REDACTED]

---

## **16. SAFETY OUTCOMES**

All outputs for safety outcomes will be based on the Safety Set.

For by visit summaries of change from baseline summaries, the last value on treatment (last assessment on or before the last dose of study medication plus one day) will be presented.

### **16.1. ADVERSE EVENTS**

Adverse Events (AEs) will be coded using MedDRA central coding dictionary currently in effect at the time of interim analysis or final Part A database lock.

Treatment emergent adverse events (TEAEs) are defined as AEs that started or worsened in severity on or after the date of the first dose of study medication and on or before the date of last dose of study medication in Part A plus one day.

All AEs with an onset date after the last dose of study medication plus one day, but before the start of Part B will be listed in the AE data listing and labelled as 'Follow-up Adverse Event'.

See [Appendix 2](#) for handling of partial or completely missing dates for AEs. In the case where it is not possible to define an AE as treatment emergent or not, the AE will be classified as the worst case, i.e., treatment emergent.

An overall summary of the number of subjects within each of the categories described in the [sub-sections 16.1.1](#) and [16.1.2](#) below will be provided as specified in the TLF shells.

Listings will include all adverse events, TEAEs and Non-TEAEs.

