3.1.1 Part A Study Periods (up to 10 Weeks, Including Screening/Baseline)

Part A of the study consists of the following periods: screening period, on-treatment period, and safety follow-up period. Patients who rollover directly into Part B will not have a unique safety follow-up visit after the 6-week treatment.

Screening Period (2 Weeks)

Potential patients will be evaluated during a screening period lasting up to 2 weeks, unless confirmed by the medical monitor that a longer screening phase, lasting no longer than 28 days, is appropriate to ensure washout of excluded medications with long half-lives (e.g., fluoxetine), under the supervision of the investigator before baseline.

After obtaining written informed consent, diagnostic interviews and physical examinations will be conducted, vital signs and ECGs will be assessed, and blood samples for laboratory assessments will be collected. Patients considered potentially eligible for participation will be required to discontinue their current antidepressant treatment and/or other psychotropic drugs.

[REDACTED]
[REDACTED]

At baseline (Visit 2), patients who continue to meet all eligibility criteria will be randomly assigned to 1 of the 3 treatment arms for a 6-week, double-blind treatment period. Patients will be randomly assigned to 1 of the following groups: 40-mg ITI-007, 60-mg ITI-007, or matching placebo.

On-Treatment Period (6 Weeks)

Patients will take their first dose of study medication the evening of their baseline randomization visit. A single dose will be taken each day in the evening for the duration of the on-treatment period.

Following randomization, patients will attend the clinic at Weeks 1, 2, 3, 4, 5, and 6.

The on-study treatment period will be a total of 6 weeks.

Safety Follow-up Period (2 Weeks)

For those patients not continuing on to Part B, a return to the clinic for a safety follow-up visit will occur at Week 8, approximately 2 weeks following the last dose of study medication. If possible, patients who discontinue treatment prematurely will be seen for an early termination visit (within 1 week of the last dose of study drug when possible) and will be asked to return to the clinic for a safety follow-up visit 2 weeks following withdrawal.

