5.1 Method of Assigning Patients to Treatment Groups

In Part A, patients who continue to meet all eligibility criteria at baseline (Visit 2) will be randomly assigned to 1 of the 3 treatment arms for a 6-week, double-blind treatment period. Patients will be randomly assigned to 1 of the following groups: 40-mg ITI-007, 60-mg ITI-007, or matching placebo. The on-study treatment period will be a total of 6 weeks.

An interactive voice response system (IVRS)/interactive web response system (IWRS) (English only) will be used to administer the randomization schedule. Unblinded biostatistics personnel not participating in the conduct of the study will generate a permuted block randomization schedule using SAS software Version 9.2 or later (SAS Institute Inc, Cary, North Carolina) for IVRS/IWRS, which will link sequential patient randomization numbers to treatment codes. In the event that the blind needs to be broken because of a medical emergency, the investigator may unblind an individual patient's treatment allocation (Section 5.6.1). The randomization schedule will be stratified by Bipolar I or Bipolar II diagnoses at screening.

Each patient will be assigned a randomization number, which will be separate from the patient identification number. Once a randomization number has been allocated to a patient, it may not be assigned to another patient.

The IVRS/IWRS will send visit notifications to the study center personnel, confirming the patient data that were entered. The IVRS/IWRS notifications should be filed securely at the study site.

In Part B, enrollment will occur on Day 43, Visit 8 which is Day 1 of Part B. If a patient is required to undergo screening (Visit 10), upon determination of his/her eligibility for Part B, the enrollment will occur on Visit 11 as indicated in the Schedule of Events. Patients will be issued treatment cards of ITI-007 (60 mg). ITI-007 will be administered orally once daily as tablet for up to approximately 6 months (175 days).

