## **7. GENERAL CONSIDERATIONS**

Relative Study Day will be calculated from the date of Day 1, which is the day of first treatment with double-blind study medication in Part A, and will be used to show the start and/or stop days of treatment, study procedures and assessments, prior, concomitant, and post-treatment medications, and adverse events.

[figure not shown]
- If the date of the treatment, procedure, or event is on or after Day 1 date then:

Relative Study Day = (date of variable of interest – Day 1 date) + 1.

- If the date of the treatment, procedure, or event is prior to the Day 1 date then:

Relative Study Day = (date of variable of interest – Day 1 date).

In the situation where the date is partial or missing, Relative Study Day, and any corresponding event durations will appear missing in the listings.

Analyses presented by visit or study day will be based on the scheduled visits as planned in the protocol. Visit windows for unscheduled visits or early discontinuation visits are defined in **Table A**, which provides the mapping of relative day ranges to the scheduled target days and the study periods for Part A. If more than one assessment is available in the same ‘Range of Relative Study Days’ (window), the assessment closest to the Scheduled Target Day will be selected and assigned to the Scheduled Target Day. If two or more assessments are available in the same window and are equidistant from the Scheduled Target Day, the latest assessment will be selected (if before study Part B start). 

Listings will include scheduled, unscheduled, retest and early discontinuation data.

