### ALGORITHM FOR TREATMENT EMERGENCE OF ADVERSE EVENTS

START DATE	STOP DATE	ACTION
Known	Known	
If start date < study medication start date or start date>study medication end date + 1 day , then not TEAE
 
If study medication start date ≤ start date ≤ study medication end date + 1 day, then TEAE

	Partial	
Impute stop date as latest possible date (i.e. last day of month if day unknown or 31st December if day and month are unknown), then:
 
If start date < study med start date or start date>study med end date + 1 day, then not TEAE
 
If study med start date ≤ start date ≤ study med end date + 1 day, then TEAE

	Missing	
If start date < study med start date or start date>study med end date + 1 day, then not TEAE
 
If study med start date ≤ start date ≤ study med end date + 1 day, then TEAE

Partial, but known components show that it cannot be on or after study medication start date or cannot be before study medication end date	Known	Not TEAE
	Partial	Not TEAE

START DATE	STOP DATE	ACTION
	Missing	Not TEAE
Partial, could be on or after study medication start date but before study med end date	Known	If stop date < study med start date, then not TEAE If stop date $\geq$ study med start date, then TEAE
	Partial	Impute stop date as latest possible date (i.e. last day of month if day unknown or 31st December if day and month are unknown), then: If stop date < study med start date, then not TEAE If stop date $\geq$ study med start date, then TEAE
	Missing	Assumed TEAE
Missing	Known	If stop date < study med start date, then not TEAE If stop date $\geq$ study med start date, then TEAE
	Partial	Impute stop date as latest possible date (i.e. last day of month if day unknown or 31st December if day and month are unknown), then: If stop date < study med start date, then not TEAE If stop date $\geq$ study med start date, then TEAE
	Missing	Assumed TEAE

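### For direct rollovers, the Part A TEAE window (last dose plus one day) takes in Day 43, which is Part B Day 1, with no cut at the first open-label dose

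*SAP*

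**What the plan says.** SAP 16.1 closes the Part A TEAE window for onsets "on or before the date of last dose of study medication in Part A plus one day". The Appendix 2 algorithm for treatment emergence applies the same rule to complete dates: "If study medication start date ≤ start date ≤ study medication end date + 1 day, then TEAE". Both compare calendar dates. Neither uses clock time or refers to the start of Part B.

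The only mention of Part B in the adverse-event text of 16.1 concerns a different category, the follow-up events: "All AEs with an onset date after the last dose of study medication plus one day, but before the start of Part B".

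On timing, Protocol 3.1.1 states "Patients will take their first dose of study medication the evening of their baseline randomization visit" and "The on-study treatment period will be a total of 6 weeks". SAP Table A likewise gives completers a 42-day course. Protocol 5.1 states "In Part B, enrollment will occur on Day 43, Visit 8 which is Day 1 of Part B". Protocol 5.4.1 has Part B treatment cards supplied at that visit, and 5.2 has every Part B patient take 60 mg in the evening.

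**The concern.** A placebo patient who rolls over directly would have a first exposure to ITI-007 on a date that still belongs to the Part A placebo window. A 40 mg patient would take a first 60 mg dose on a date that belongs to the 40 mg window. SAP 6.5 groups safety patients by the treatment received, or by the one most often received if dosing was incorrect, so one open-label dose does not move a patient out of the Part A arm.

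This matters because the Part A tables are comparative. SAP 16.1.1 plans relative risks with confidence intervals and chi-square p-values for any TEAE and for each preferred term and organ class. Where the drug raises the risk of an event, open-label onsets counted under placebo make the drug look closer to placebo. In a safety comparison that is the unfavourable direction. Preferred-term rows with few events are the most sensitive.

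**Working it through.** **Dates for a direct rollover**

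- Doses in Part A: 6 weeks × 7 = 42, the first on Day 1 (Protocol 3.1.1). This agrees with the 42 days in SAP Table A.
- Last Part A dose: Day 1 + 42 − 1 = Day 42.
- End of TEAE window: Day 42 + 1 = Day 43 (SAP 16.1, Appendix 2).
- Start of Part B: Day 43 (Protocol 5.1).
- Overlap: one calendar date.

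The overlap does not depend on Visit 8 falling exactly on Day 43. If the last Part A dose is on day L and Part B starts on L + 1, the window also ends on L + 1. This was checked for L = 40 to 44.

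**Hours exposed on that date**

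Protocol 5.2 gives dosing hours of 20:00 to 22:30 for Part A and only the evening for Part B. Assuming the same hours in Part B, the time from dose to midnight is 24 − 22.5 = 1.5 hours to 24 − 20 = 4 hours. The other 20 to 22.5 hours of Day 43 precede the open-label dose and belong to Part A.

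**Does another rule close the gap?**

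- Follow-up events (SAP 16.1): these begin after last dose + 1 day, so the Part B limit there does not reach a Day 43 onset.
- Week 6 visit window (SAP Table A) and post-treatment medications (SAP 13): both stop at the start of Part B. The SAP therefore makes this cut elsewhere.
- Appendix 2, partial or missing start dates: a partial date that could fall within Part A dosing, or a missing one, becomes a TEAE if the event had not stopped before study drug began. There is no Part B limit here either, so an open-label event dated only to the month containing Day 42 could be classed as Part A.

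**Can the number of events be estimated?**

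No. It needs the share of placebo patients who roll over directly and the share of those with a same-evening onset, and the documents give neither. With 183 per arm and purely assumed values, 183 × 0.25 × 0.005 = 0.2 patients and 183 × 0.75 × 0.05 = 6.9 patients. The assumptions decide the answer, so neither figure is offered as an estimate.

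**Protocol window**

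Protocol 7.5.8 uses last dose + 14 days. Without a Part B cut it would reach Day 42 + 14 = Day 56 and overlap Days 43 to 56, which is 14 dates. The SAP's shorter window removes most of that overlap and leaves one date.

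**The case against.** The one-day extension has a sound purpose. A reaction to the Day 42 evening dose can appear overnight or the next morning, and most of Day 43 does precede any open-label dose. That stands: Day 43 should not simply be removed from Part A.

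The Day 43 open-label dose is an inference. It rests on the Part B Day 1 label, the dispensing at Visit 8 and evening dosing, and the schedules of events are not visible. This also stands. The inference is reasonable but should be worded as one.

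The tables count patients, not events. A placebo patient who already had a TEAE adds nothing to the overall rate, and a repeat of the same preferred term adds nothing to that row. This stands, and it limits the effect further.

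The Part B SAP or the table shells might settle the attribution. Neither can be seen. They would also have to depart from a Part A rule that is explicit as written, so this does not remove the point.

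Finally, separating events by clock time may not be workable. Doses are taken at home, SAP 14 describes the dosing form only by dates, and Protocol 6.3.1.7 records onset time only if known. This stands, and it shapes the fix.

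**Conclusion.** The gap is real and follows from the stated rules: the Part A TEAE window includes the first day of Part B for direct rollovers, with no cut at the first open-label dose. It assumes that this dose is taken on the evening of Day 43. Patients re-screened into Part B later are not affected by the one-day rule.

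The effect is probably small. It covers about 1.5 to 4 hours in a subset of patients if the Part A dosing hours carry over, plus any events with incomplete start dates. It touches the Part A safety comparisons and leaves the primary and key secondary analyses alone.

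A reader might infer that the placebo TEAE rate is inflated by several percentage points. The documents do not support this, because they give no rollover rate or same-evening onset rate and because patients who already had a TEAE are not counted again. A reader might also infer that all Day 43 events of uncertain timing should leave the Part A arms. That would discard genuine Part A events and reverse the worst-case rule in SAP 16.1.

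**What to change.** In SAP 16.1, and in the Appendix 2 rows for known, partial and missing start dates, define a Part A TEAE as one with onset on or before the last Part A dose plus one day **and** before the first Part B dose.

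For a Day 43 onset in a direct rollover:

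- Assign the event to Part B only when recorded information shows it began after the first open-label dose, such as an onset time or an eCRF indication of the order.
- If the order is unknown, keep the event as a Part A TEAE under the existing worst-case rule and flag it in the listing.
- Repeat the TEAE summary without the flagged events as a sensitivity check.

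Handle partial and missing start dates in direct rollovers the same way. When editing these sections, also reconcile the one-day window with the 14-day window in Protocol 7.5.8.

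The cost is a short SAP edit, one programming condition, one flag and one repeated summary. The Part B start date is already needed for the Week 6 window and the post-treatment medication rule.

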#### **16.1.1. AEs AND TEAEs**

The incidence of TEAEs will be presented by SOC and PT and also broken down further by maximum severity and relationship to study medication.

The number and percentage of subjects with at least one TEAE and total number of subjects having events for each PT and SOC will be summarized. A summary of TEAEs will be provided with only PTs and a separate summary for only SOCs. An additional summary of TEAEs will be provided for PTs occurring in at least 5% of subjects in any treatment group (ITI-007 60 mg, ITI-007 40 mg, or placebo). This summary will be repeated for TEAEs possibly related (possibly, probably, or definitely) to study drug. Within each subject, multiple reports of events that map to a common MedDRA PT and/or SOC will be condensed into a single AE for incidence counts. Summaries will be presented by treatment group and in decreasing frequency by decreasing dose group (ITI-007 60 mg, ITI-007 40 mg) and placebo group. AEs which occur during the follow-up period will be summarized by PT and SOC and treatment group.

---

The relative risk of at least one TEAE and for each PT and SOC will also be presented along with 95% CIs and p-values obtained by the Chi-square test for association.

Intensity is classed as “not specified”, “mild”, “moderate”, “severe”, or “life-threatening” (increasing severity). AEs and TEAEs with a missing severity will be classified as “not specified”. If a subject reports a TEAE more than once within the same PT and SOC, the event with the worst case severity will be used in the corresponding severity summaries.

Relationship, as indicated by the Investigator, is classed as “not specified”, “unrelated”, “unlikely to be related”, “possibly related”, “probably related”, or “definitely related” (increasing severity of relationship). A “related” TEAE is defined as a TEAE with a relationship to study medication as “possibly related”, “probably related”, or “definitely related” to study medication. TEAEs with a missing relationship to study medication will be regarded as “related”. If a subject reports the same AE more than once within the same PT and SOC, the AE with the worst case relationship to study medication will be used in the corresponding relationship summaries. A summary of related TEAEs by SOC and PT will be presented.

AEs leading to early withdrawal or discontinuation of study medication will be identified by using the Adverse Events page of the eCRF, where item ‘Action taken with study treatment’ indicates permanent discontinuation of study medication, i.e., “Drug withdrawal”. AEs leading to early study withdrawal will be identified by using the Adverse Events page of the (e)CRF, where the answer to item ‘Did the AE cause the subject to discontinue from the study?’ indicates “Yes”.

For AEs leading to early study withdrawal or discontinuation of study medication, summaries of incidence rates (frequencies and percentages) by SOC and PT will be prepared.

